9.2. Efficacy Analysis

Not Applicable.

9.3. Analysis of Other Endpoints

Not Applicable.

9.4. Safety Analysis

9.4.1. Analysis of Primary Endpoint

- **Definition:** The primary endpoint is the proportion of subjects with a decrease in the threshold value from baseline to termination in five or more points (in either eye) at the $p < .05$ level repeated in the same five points on subsequent computerized automated perimetry testing (Humphrey 24-2 SITA standard).
- **Baseline:** Baseline is determined from the last VFTs prior to receiving investigational product. A point will be considered abnormal at baseline only if it was abnormal (< 0.05) at both baseline tests.
- **Termination:** Termination is the VFT done at Week 12 (including a repeat test if applicable). For subjects who did not complete the study, the last available test(s) after Day 1 will be used. Data will not be imputed for subjects who do not have any VFTs after baseline; rather, such subjects will be treated as missing values.
- **Comparison:** The difference in proportions between pregabalin and placebo will be compared using a 2-sided 95% confidence interval (CI). Non-inferiority will be demonstrated if the upper CI bound is less than 0.10 (10%).
- **Populations:** The intent-to-treat (ITT) population is defined as all subjects randomized to treatment who received at least one dose of investigational product. The Per Protocol population is a subset of the ITT population, and excludes subjects who had a decrease in at least 5 points at termination but did not return for a repeat test. The Per Protocol population may also exclude subjects with major protocol violations; the list of subjects excluded will be determined prior to breaking the blind. The primary analysis will be performed on the Per Protocol population, the expectation is that the Per Protocol subset will be close in the number of subjects to the number of subjects randomized. A supplementary analysis of the primary parameter will be performed using the ITT population.

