4.2. Statistical Decision Rules

The difference in proportions between pregabalin and placebo will be compared using a 2-sided 95% confidence interval (CI). Non-inferiority will be demonstrated if the upper CI bound is less than 0.10 (10%).

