5. ANALYSIS SETS

5.1. Full Analysis Set

The Full Analysis Set (referred to in the protocol as the intent-to-treat (ITT) population) is defined as all subjects randomized to treatment who received at least one dose of study medication.

Since data will not be imputed for patients who do not have a baseline or for patients who do not have post-baseline data for a specific parameter, such patients will not appear in the FAS analyses for that parameter. Subjects who had a decrease in at least 5 points at termination but did not return for a repeat test will be included in the FAS set and will be assumed to have a confirmed decrease for VFT analysis. Termination is the VFT performed at Week 12 or the last available post-treatment VFT for subjects who did not complete the study (per Protocol Section 9.4.1).

5.2. 'PER PROTOCOL' Analysis Set

The primary analysis will be performed on the Per Protocol population.

The Per Protocol population is a subset of the ITT population, and excludes subjects who had a decrease in at least 5 points at termination but did not return for a repeat test. The Per Protocol population may also exclude subjects with major protocol violations; the list of subjects excluded will be determined prior to breaking the blind. The expectation is that the PP subset will be close in the number of subjects to the to the number of subjects randomized.

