5.3. Safety Analysis Set

In this study, all parameters to be analyzed are safety parameters. The primary analysis of the primary parameter will be performed using the Per Protocol population, with a supplementary analysis that uses the ITT population. All other safety data will be summarized using the ITT population.

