5.6. Protocol Deviations

The list of protocol deviations will be compiled prior to database closure. Subjects who *had a decrease in at least 5 points at termination* (the Week 12 VFT or last available post-treatment VFT) *but did not return for a repeat test* will be excluded from the Per Protocol population, as will patients with certain protocol deviations (to be determined based on clinical judgment prior to breaking the blind).

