8.2. Statistical Analyses

8.2.1. Primary Analysis

The primary endpoint will be analyzed using a non-inferiority analysis. The difference in proportions between pregabalin and placebo in the per protocol population will be compared using a 2-sided 95% confidence interval (CI). Non-inferiority will be demonstrated if the upper CI bound is less than 0.10 (10%).

The primary analysis is based on the Per Protocol set and the primary endpoint proportion of patients with visual field deterioration. A 2-sided 95% confidence interval on the difference in proportions between pregabalin and placebo will be constructed using unconditional exact methods. To support interpretation of the primary analysis, an analysis as described above but based on the ITT population rather than the Per Protocol set, will be performed. In this analysis, patients with a decrease in ≥ 5 points at termination but no repeat visit will be treated as if they did have a repeat visit that confirmed the decrease.

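### Non-inferiority is decided on a Per Protocol set that drops subjects with a new 5-point field loss and no repeat test, and no rule covers disagreement with the ITT analysis that counts them

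*Protocol*

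**What the plan says.** Protocol 9.4.1 and SAP 5.2 put the primary analysis on the Per Protocol population, and the Protocol Summary (Statistical Methods) and SAP 8.2.1 apply the 10% upper bound to it. SAP 4.2 states the bound without naming a population.

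The Per Protocol set "excludes subjects who had a decrease in at least 5 points at termination but did not return for a repeat test" (Protocol 9.4.1). SAP 5.6 repeats that such subjects "will be excluded from the Per Protocol population", and SAP 7 agrees. Major protocol violators may also be excluded, from a list fixed before unblinding.

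In the ITT (full analysis) set the same subjects "will be included in the FAS set and will be assumed to have a confirmed decrease for VFT analysis" (SAP 5.1; likewise SAP 7 and 8.2.1). Patient 5 in SAP A.1.2 shows the contrast: excluded from the primary analysis, deteriorated in ITT. Protocol 9.4.1 does not say how ITT treats a missed repeat.

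On the role of ITT, the protocol says "A supplementary analysis of the primary parameter will be performed using the ITT population", and SAP 5.3 says "The primary analysis of the primary parameter will be performed using the Per Protocol population, with a supplementary analysis that uses the ITT population". SAP 8.2.1 offers it as support for interpretation and SAP 8.2.5 as a robustness check. Neither document says what follows if the two analyses disagree.

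**The concern.** A subject with no new 5-point loss at termination needs no repeat and stays in the Per Protocol set. A subject with such a loss stays in only if the repeat is done. The exclusion is therefore triggered by a first positive result and can take out possible events but never a clear non-event. Listing exclusions before unblinding prevents selection by arm; it does not prevent selection by outcome.

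In a safety trial, fewer events on the test drug help the claim. The exclusion favours the claim if repeats are missed equally in both arms or more often on pregabalin, and works slightly against it if only placebo subjects miss them. Events are expected to be few, so a handful of subjects could decide the result. As written, non-inferiority would be declared on Per Protocol even if the ITT bound exceeded 10%.

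**Working it through.** **Inputs.** 187 subjects randomised 1:1, taken as 93 pregabalin v 94 placebo; 1% event rate per arm; margin 10%; two-sided 95% interval (Protocol 3, 9.1; SAP 2.3, 4.2); unconditional exact method (SAP 8.1). The missed-repeat rate *m* and the rate *u* of first losses that a repeat would not confirm are not in the documents and are assumed.

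**1. The plan's own power figure.** With 93 per arm and the normal approximation, SE = √(2 × 0.01 × 0.99 / 93) = 0.01459; 0.10 / 0.01459 − 1.96 = 4.89; power 99.99995%. This reproduces the stated >99.9%. Exact enumeration gives 99.3%.

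**2. How few events decide.** The upper bound is the difference *d* at which the one-sided p-value is 0.025. The test uses the score statistic (p̂₁ − p̂₂ − d) / √(p̃₁(1−p̃₁)/n₁ + p̃₂(1−p̃₂)/n₂), where p̃₁ and p̃₂ are estimated under p̃₁ − p̃₂ = d and the p-value is maximised over the nuisance proportion. At 93 v 94, the largest pregabalin count that still meets the bound is 3, 4, 4 and 5 for placebo counts of 0, 1, 2 and 3. So 4 v 0 and 5 v 1 fail.

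| Confirmed events | Missed repeats | Per Protocol upper bound | ITT upper bound |
|---|---|---|---|
| 0 v 0 | 4 v 0 | 0/89 v 0/94: 4.2% | 4/93 v 0/94: 10.7% |
| 1 v 1 | 4 v 0 | 1/89 v 1/94: 5.2% | 5/93 v 1/94: 11.1% |
| 3 v 0 | 1 v 0 | 3/92 v 0/94: 9.4% | 4/93 v 0/94: 10.7% |

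Four missed v none is extreme. At 1% with no unconfirmed losses, 93 × 0.01 = 0.93 first losses are expected on pregabalin. At 12% (1% plus an assumed 11% unconfirmed), 93 × 0.12 = 11.2 are expected, and 4 / 11.2 is about 36% missed against none on placebo.

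**3. False-claim rate at the margin.** True rates are 11% v 1%. With nothing missed, sum P(placebo = y) × P(pregabalin ≤ limit for y):

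- y = 0: 0.3888 × 0.00634 = 0.00247
- y = 1: 0.3692 × 0.01973 = 0.00728
- y = 2: 0.1734 × 0.01973 = 0.00342
- y = 3: 0.0537 × 0.04918 = 0.00264

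The subtotal is 0.01581; y ≥ 4 adds 0.0009, giving 1.67%.

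With missed repeats, in each arm M ~ Bin(n, (p+u)m) and confirmed events E given M ~ Bin(n−M, p(1−m) / (1−(p+u)m)). Per Protocol uses E/(n−M) and ITT uses (E+M)/n. The exact region is recomputed for each reduced n, by full enumeration. With equal missing and u = 0:

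| Missed | Per Protocol | ITT | Both required |
|---|---|---|---|
| 0% | 1.67% | 1.67% | 1.67% |
| 5% | 2.28% | 1.67% | 1.63% |
| 7% | 2.54% | 1.67% | 1.62% |
| 10% | 2.97% | 1.67% | 1.61% |
| 20% | 4.99% | 1.67% | 1.60% |

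- With u = 11%, Per Protocol passes 2.5% at about 9% missed (2.54%).
- Missed on pregabalin only, 10% v 0%: 3.18%. On placebo only, 0% v 10%: 1.57%.
- With a Newcombe limit instead (400,000 simulated trials, 93 per arm), Per Protocol gives 2.4%, 3.3% and 6.0% at 5%, 10% and 20% missed.

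**4. How often Per Protocol claims and ITT does not.** At 5%, 10% and 20% missed with u = 0: 0.1%, 0.2% and 0.4% at true rates 1% v 1%; 4.0%, 7.6% and 14.7% at 5% v 1%. With u = 11% at 1% v 1% (simulation, Newcombe limit): 1.8%, 4.3% and 10.5%.

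**The case against.** Much of this is already in hand. The exclusion is disclosed, the worst-case ITT counterpart is specified in several SAP sections, and it will be reported with the same type of interval. Protocol 7.1.4 calls for a repeat within 2 weeks of the central reader's confirmation, and both documents expect the Per Protocol set to be close in size to the number randomised. Whether ITT is supportive or decisive is partly a design choice. These points limit the probable effect, but they give ITT no role in the claim. Nor is a near-complete set enough protection: four subjects are about 2% of 187.

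A missed repeat is also not a proven event, because the endpoint requires confirmation in the same points. If 11% per arm had unconfirmed first losses, about 11 of every 12 first losses at a 1% event rate would not confirm, and ITT would count mostly noise. That stands. It is why ITT should not simply replace Per Protocol: with 10% v 30% missed and u = 11%, the false-claim rate at 11% v 1% is 5.75% for ITT alone, 2.41% for Per Protocol and 1.73% if both are required.

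A reader might infer that the trial's error rate is materially inflated, or that the exclusion always favours pregabalin. The documents support neither: they give no missed-repeat rate, and placebo-only missing slightly lowers the false-claim rate. Nor is a Per Protocol claim at 5% v 1% false, since that true difference lies inside the margin.

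**Conclusion.** The point holds as a gap in the decision rule. The deciding analysis drops subjects because of an unresolved first positive result, and nothing says what happens if the analysis that counts them fails. A few subjects could reverse the conclusion, but the expected effect is small. With equal missing and every loss confirming, the Per Protocol false-claim rate stays within 2.5% up to about 7% missed, then reaches about 3.0% at 10% and 5.0% at 20%. At the planned 1% v 1%, with no unconfirmed first losses, the analyses disagree in this direction in only 0.1 to 0.4% of trials. All these figures rest on assumed missed-repeat rates. It would go too far to say that the ITT result is ignored: it will be reported and can be weighed, but it has no formal force. The gap should be closed, since the remedy uses only analyses already planned.

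**What to change.** Before the blind is broken:

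- In the Protocol Summary (Statistical Methods), Protocol 9.4.1, SAP 4.2 and SAP 8.2.1, claim non-inferiority only if the upper bound is below 10% in both the Per Protocol and the ITT analysis.
- Add to Protocol 9.4.1 the rule, now only in the SAP, that a missed repeat counts as confirmed in ITT.
- Align SAP 5.3 and the ITT row of SAP 8.2.5.
- Report missed repeats by arm.
- Restate the primary-endpoint power in Protocol 9.1 and SAP 2.3 for the joint rule.

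Across 75 combinations of missed rates (0 to 30% per arm) and unconfirmed losses (0, 5 and 11%), the joint rule's false-claim rate at 11% v 1% is at most 1.73%.

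**Cost.** No new data or analysis is needed, but the success rule changes, so both documents need amending. Power of the joint rule at 1% v 1%, equal missing:

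| Unconfirmed first losses per arm (assumed) | 5% missed | 10% missed | 20% missed |
|---|---|---|---|
| none | 99.3% | 99.3% | 99.3% |
| 5% | 98.6% | 97.8% | 95.7% |
| 11% | 97.6% | 95.1% | 88.2% |

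The 11% is the 12% placebo field-change rate in Protocol 1.1, whose definition is not given there, less the planned 1%. Subjects with no field test after baseline remain outside both analyses; this change does not address them.

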9.4.2. Analysis of Secondary Endpoints

9.4.3. Mean Deviation

Change in mean deviation from baseline to termination will be computed for each subject. Baseline mean deviation will be the average of the two mean deviations from the Baseline visit, and termination mean deviation will be the mean deviation at the Week 12 visit (or the last available after Day 1 for subjects who terminate early). If a repeat test was done at termination, the mean deviation from the repeat test will be used. For each subject, the worst eye (ie, the eye with the greatest decrease in mean deviation) will be used in the analysis. Change in mean deviation will be analyzed for the ITT population using analysis of covariance (ANCOVA), with treatment and center in the model and the baseline mean deviation as the covariate. Least squares means will be obtained from the model and a

2-sided 95% confidence interval will be constructed on the difference in least squares means between pregabalin and placebo. Non-inferiority with respect to mean deviation will be demonstrated if the lower bound of the CI is greater than -2.0 dB.

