2.2. Endpoints

Primary endpoint:

- The proportion of subjects with a decrease in the threshold value from baseline to termination in five or more points (in either eye) at the $p < .05$ level repeated in the same five points on subsequent computerized automated perimetry testing (Humphrey 24-2 SITA standard).

Secondary endpoints:

- Change in mean deviation score from baseline to Week 12 from the Humphrey threshold test;
- Change in visual acuity from Baseline to Week 12 expressed by number identified in ETDRS visual acuity assessment.

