5.4.2. Preparation and Dispensing

The Sponsor will provide the investigational product that will be dispensed according to randomization code. The investigator must verify and acknowledge the receipt of clinical drug supplies and retain related documentation. A set of detailed dispensing instructions will be provided.

At Randomization, each subject will receive 1 bottle of investigational product capsules with the titration dose for the first week (pregabalin 75 mg BID (150 mg/day) or placebo BID). At Week 1, the subject will receive 5 bottles containing capsules of the treatment dose (pregabalin 150 mg BID (300 mg/day) or placebo BID). At Week 6, the subject will receive 6 bottles containing capsules of treatment dose (pregabalin 150 mg BID (300 mg/day) or placebo BID). At Week 12, the subject will receive 1 bottle containing capsules for the taper (pregabalin 75 mg BID (150 mg/day) or placebo BID). All bottles will contain 3 days overage except the taper bottle that will contain only enough capsules for seven days.

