7.1.4. Visual Field Test

All investigators will receive extensive training at the investigator's meeting and periodically throughout the study to improve the reliability of measurements by monitoring subject compliance and recognizing artifact in visual field examination. Investigators should repeat/reschedule sessions when subjects have poor compliance or any difficulties which interferes with visual field testing. Ophthalmologists/ VFT technician should inquire prior to testing when the subject's last seizure occurred to assess the possibility of ictal or post-ictal state to avoid interference with testing; the time of last dose of investigational product (it is

recommended that the subject withholds the morning dose of investigational product until after the VFT has been completed to reduce any potential effects of CNS events that may occur (eg, somnolence) with pregabalin which may interfere with testing). If the subject has taken the morning study dose of medication, testing should be performed when the subject is least probably affected by any potential CNS events that may occur to ensure the subject is optimally alert during the test.

Prior to performing the computerized automated perimetry (Humphrey 24-2 SITA), pupil size will be measured and recorded and must be 3 mm or greater for VFT, otherwise the pupil must be dilated. Visual fields will be measured using the Humphrey 24-2 SITA and analyzed using STATPAC according to the guidelines. A detailed guideline is provided in the [Appendix 2](#) of this document. Because visual field results are strongly affected by experience, visual field tests will be repeated on two occasions at Screening and at Baseline visits. A pre-test is recommended for all subjects who have never performed VFT.

All automated perimetry results will be read by a central reader within 3 working days of the examination. If the central reader assesses the visual field exam to be of poor quality, the exam should be repeated as soon as possible within 2 weeks of being notified. The repeat test will be performed only on the eye whose test was considered to give a poor result.

Any subject who has a new loss of sensitivity at the $p < .05$ level in five or more points in the visual field will have a repeat exam as soon as possible within 2 weeks of receiving confirmation from the central reader.

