9. DATA ANALYSIS/STATISTICAL METHODS

9.1. Sample Size Determination

The study will be powered to show non-inferiority of pregabalin with respect to placebo on the mean deviation score from the Humphrey threshold test, a secondary endpoint. Non-inferiority from placebo will be declared with respect to mean deviation if the lower bound of the 95% 2-sided confidence interval of the difference in mean deviation scores between pregabalin and placebo is greater than -2.0 decibels (dB). Assuming the mean deviation scores to be equal and assuming estimated common standard deviation of 1.3 dB, then the proposed sample size of 187 subjects will provide greater than 85% power to show non-inferiority of pregabalin to placebo.

The estimated common standard deviation of 1.3 dB, from the 15 March 2019 dataset prepared for the annual Internal Review Committee (IRC) blinded review (refer to [Section 9.6](#)), was used to re-estimate the sample size for the secondary endpoints. Previously, at the time of study design, a common standard deviation of 5.6 dB had been used for the sample size determination based on literature.¹² Table 1 below used common standard deviation (1.3) and the number of enrolled subjects (n=187) to estimate the study power.

Table 1. Study 1096 Sample Size and Power for the Secondary Endpoint

Total Number of enrolled subjects	Common Standard Deviation	Non-inferiority Margin	Power
187	1.3	-2.0	>99.9%

For the primary endpoint, the proposed sample size will provide >99.9% power to show non-inferiority of pregabalin to placebo with respect to the proportion of subjects with a repeated decrease in the same 5 visual field points, with non-inferiority declared if the upper bound of the 95% confidence interval for the difference between pregabalin and placebo does not exceed 10% and assuming a proportion of subjects meeting primary endpoint definition of 1% for both groups. Table 2 below provided the estimated power for the primary endpoint.

Table 2. Study 1096 Sample Size and Power for the Primary Endpoint

Total Number of enrolled subjects	Proportion of Subjects Meeting Primary Endpoint Definition	Non-inferiority Margin	Power
187	1%	10%	>99.9%

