It is the responsibility of central reader/reading center to ensure VFTs are collected properly and accurately. The central reader /reading center is responsible for:

Training

- All investigators and staff who will perform study procedures will receive extensive training. Refresher training may be offered periodically throughout the study as needed;
- Completion of training and approval of perimetrist will be documented;
- Investigator and staff will not perform the tests until they have been certified by central reader.

During the study, the center reader performs the following:

- Confirms VFT outcomes and decides if a repeat is necessary. This result will be communicated to the site within 72 hours of receiving test results;
- Review VFT conduct and quality control on a monthly basis. Communicate results with the sponsor. Implement improvement measurements as necessary;
- Tabulated (post-processed) data will be electronically transferred to Pfizer from the Central Reader for storage and data analysis as specified in Statistical Analysis Plan (SAP).

Appendix 3. Clinical Protocol Amendment 1

Current Amendment:

Amendment No.	Date	Country (ies)	Site(s)
1	17 October 2006	All	All

SUMMARY

Reason(s) for Amendment

The protocol section(s) that have been amended and the details of the changes are summarized in the following sections.

Protocol Section(s) Amended

The protocol sections that were amended are detailed below. The format is as follows:

- The “change from” section represents the current text in the protocol. Bolded text is used to indicate the addition of information to the current text, and strike-out of text (eg, ~~text~~) is used to show the deletion of information from the current text.
- The “change to” section represents the revised text, with the revisions shown in the “change from” section in normal text.

1. Summary and Section 3, Trial Design

Change From

A total of 284 subjects will participate in the study, 142 randomized to pregabalin, 142 to placebo. Approximately ~~10~~**15** centers will be selected that have the capability to perform the comprehensive visual field testing.

Change To

A total of 284 subjects will participate in the study, 142 randomized to pregabalin, 142 to placebo. Approximately 15 centers will be selected that have the capability to perform the comprehensive visual field testing.

2. Section 4.1, Inclusion Criteria

Change From

6. Be 18 to 65 years old and weigh ≥ 50 kg (110 lb) with BMI 18–32;

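### Week 12 mean deviation is replaced by a repeat that, quality failures aside, only low valid fields trigger; near the margin this can favour non-inferiority

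*Protocol*

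**What the plan says.** **The rule.** Protocol 2.2 defines the secondary endpoint as "Change in mean deviation score from baseline to Week 12 from the Humphrey threshold test". Protocol 9.4.3 then sets which field supplies the termination value: "If a repeat test was done at termination, the mean deviation from the repeat test will be used". SAP 6.2 and 8.2.2 repeat this. None of the three places separates a repeat done because the field was unreliable from one done to confirm a loss.

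**When a repeat is done.** Protocol 7.1.4 gives two reasons. One is poor quality as judged by the central reader. The other needs no quality failure: a subject with new loss at the 5% level in at least five points "will have a repeat exam as soon as possible within 2 weeks of receiving confirmation from the central reader".

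**Timing.** Protocol 7.1.4 says "All automated perimetry results will be read by a central reader within 3 working days of the examination". Appendix 2 says of the reader's decision: "This result will be communicated to the site within 72 hours of receiving test results". Protocol 5.4.2 says "At Week 12, the subject will receive 1 bottle containing capsules for the taper", and that bottle holds seven days' supply. No section holds the taper for a pending repeat.

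**Analysis.** SAP A.1.1 assigns field visits, repeats included, from the central reader's labels together with the treatment dates. It drops Week 15 assessments and, for early terminators, those about two weeks after stopping. It sets no cut-off for a completer's repeat. SAP 8.2.5 lists one mean deviation analysis and none on the first valid Week 12 field.

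**The concern.** Confirmation by repeat belongs to the primary endpoint, where Protocol 9.4.1 makes the repeat part of termination. Applied to mean deviation, it acts on one side only. A subject whose valid field reads low is retested and the low value is dropped; a subject whose valid field reads high is never retested. The replacement value regresses towards the mean. It is also taken under different exposure: as scheduled, either on the half-dose taper or off drug.

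Protocol 9.1 says the study is powered on mean deviation, with a formal non-inferiority test at -2.0 dB. If pregabalin lowers the field, more pregabalin than placebo subjects meet the trigger, so the rule shrinks the observed difference. At stake is the error rate of that test when the true loss lies near the margin.

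**Working it through.** **1. The plan's own figure.** Inputs from Protocol 9.1: SD 1.3 dB, 187 subjects (93 v 94), margin -2.0 dB, two-sided 95% interval, true difference 0. The SD is described thus: "The estimated common standard deviation of 1.3 dB, from the 15 March 2019 dataset prepared for the annual Internal Review Committee (IRC) blinded review".
- SE = 1.3 × sqrt(1/93 + 1/94) = 0.190 dB.
- Half-width = 1.973 × 0.190 = 0.375 dB.
- Power = Phi((2.0 - 0.375)/0.190) = Phi(8.55), above 99.9%. This reproduces Table 1; the stated power is not in question.

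**2. Effect of a bias b towards zero at a true -2.0 dB.** P(non-inferiority) = Phi((b - 0.375)/0.190).

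| b (dB) | False non-inferiority |
|---|---|
| 0 | 2.5% (nominal) |
| 0.1 | 7% |
| 0.2 | 18% |
| 0.3 | 35% |

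These error rates use only the documents' values; the sizes of b are chosen for illustration.

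**3. Where b could come from.** The documents give no trigger rate, test-retest SD, reversal fraction or repeat timing, and do not say whether a confirmatory repeat covers one eye or both. As a proxy for the point-count trigger, suppose a repeat is done when the first value falls below a cut-off c. Let rho be the correlation between the first and repeat values, and r the share of the loss cleared by the repeat. For an arm with true change mu, and a = (c - mu)/SD:

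E[used value] = mu - Phi(a) × r × mu + SD × (1 - rho) × phi(a)

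Example with c = -2.0 dB, rho = 0.5, r = 0:
- Pregabalin, mu = -2.0: a = 0, shift 1.3 × 0.5 × 0.399 = 0.26 dB.
- Placebo, mu = 0: a = -1.54, shift 1.3 × 0.5 × 0.122 = 0.08 dB.
- Observed difference = -2.0 + 0.26 - 0.08 = -1.82 dB.
- With r = 0.25, add 0.5 × 0.25 × 2.0 = 0.25 dB, giving -1.57 dB.

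Over c = -1.3, -2.0 and -2.6 dB and rho = 0.5 and 0.8, at a true -2.0 dB:

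| Loss cleared by the repeat | Observed difference (dB) | Non-inferiority declared |
|---|---|---|
| None | -1.80 to -1.97 | 3-18% |
| A quarter | -1.57 to -1.76 | 24-62% |
| Half | -1.23 to -1.60 | 56-98% |

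A two-eye, worst-eye simulation (4,000 trials, 93 per arm, between-eye correlation 0.6, cut-offs -2.0 to -3.2 dB) gave 4-19%, 24-78% and 64% to over 99%. Using the first valid field gave 2.1-2.8%.

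**4. Away from the margin.** With mu = 0 in both arms the shifts are equal and cancel. At a true -1.0 dB, Phi((1.0 - 0.375)/0.190) = Phi(3.29), about 99.9% without the overwrite and no lower with it. Only the estimate shrinks.

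**5. Timing.** Three working days are 3 to 5 calendar days. Adding 14 gives an outer limit of 17 to 19 days after Week 12. Subtracting the 7-day taper gives 10 to 12 days after the last dose. If repeats were spread evenly over the 14 days, 4/14 = 29% (3-day reading) or 2/14 = 14% (5-day reading) would fall in the taper. A prompt repeat would fall there.

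**6. Does the primary endpoint catch such a loss?** In simulations with 4-12% of placebo subjects triggering, a loss at the margin that was persistent to half cleared, and a Newcombe upper bound standing in for the exact interval, the primary endpoint met its 10% criterion in at most 7% of trials.

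**The case against.** The rule is pre-specified, reads the same in three places and applies to both arms. The repeat also supplies the termination value for visual acuity (Protocol 9.4.4). An unstated rationale is not an error, and nothing here contradicts another section. That stands. The protocol also tries to keep transient drowsiness out of field testing, and trusting a repeat over an abnormal first field fits that aim. This stands only in part: the quality criteria already deal with unreliable fields, and the advice to withhold the morning dose covers the Week 12 test itself.

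The SAP does refer to treatment dates when assigning repeats, and the late end of the repeat window runs into the Week 15 window (21 ± 3 days after Week 12), whose assessments are excluded. But no cut-off follows for a repeat labelled as such.

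Two stronger readings are tempting, and the documents support neither. A reader might infer that the repeat usually falls in the taper. The permitted window extends well past it, so the most that can be said is taper or off drug, which makes the exposure mismatch no smaller. A reader might also take the higher simulated error rates as expected. They need a true diffuse loss at the margin and a reversal fraction that no section supplies. Protocol 9.1 also does not say whether 1.3 dB is the SD of worst-eye change after replacement.

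The primary endpoint would nearly always fail first when a loss at the margin is persistent to half cleared. That stands too, though this protection weakens as clearing approaches completeness, because the primary endpoint needs confirmation on the same repeat. Week 6 fields offer a descriptive check, but with no margin or test, and they miss a later loss.

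**Conclusion.** The point holds as a cheap improvement. The replacement is unconditional and one-sided, and as scheduled it moves the measurement away from full-dose Week 12. It creates no between-arm bias without a drug effect and does not change the decision at -1.0 dB. For a diffuse loss near -2.0 dB it favours non-inferiority: modestly if the loss persists (about 1-10% understatement in the analytic model), materially only if part of the loss clears by the repeat. The firm statement is the sensitivity of the test: 0.2 dB of bias at the margin takes the error from 2.5% to 18%. The actual bias is unknown. The consequence is mostly confined to this secondary test, and the documents do not support the view that the trial's overall conclusion is unsafe.

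**What to change.** Before unblinding, in Protocol 9.4.3 and SAP 6.2, 8.2.2 and A.1.1:

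- Take termination mean deviation from the Week 12 field if it met the central reader's quality criteria. For early terminators, use the last field recorded after Day 1 under the existing rule and A.1.1 exclusions, on the same quality condition. Let a repeat replace the field only after a quality failure.
- Keep the repeat-based value as a sensitivity row in SAP 8.2.5. If the main definition is not to be changed this late, at least add the first-valid-field analysis as a pre-specified sensitivity row.
- Report confirmatory repeats by arm and by timing relative to the taper.
- State whether the parallel visual acuity rule (Protocol 9.4.4, SAP 8.2.2) is to be aligned, so that the two secondary endpoints do not use different days unintentionally.

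Leave the primary endpoint's confirmation rule and all dosing unchanged.

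The cost is wording and a small derivation change on data already collected. Some noisy low readings stay in both arms, and the SD rises by about 2-11% in simulation (1.3 × 1.11 = 1.44 dB at most). At an SD of 1.45 dB the SE is 0.212 dB and power at zero difference remains above 99.9%.
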